## **9.6. Selection of Doses and Administration in the Study**

The dosing regimen of diclofenac [REDACTED] mg in a patch size of [REDACTED] applied [REDACTED] and rotated between 2 sites on the target knee, inner and outer sides, is based on the following considerations and rationale:

- A dose that targets diclofenac exposure after HP-5000 patch application that is similar to that of registered topical diclofenac products and considerably lower than that of oral diclofenac tablets.
- Previously completed clinical studies using the same size patch showed no issue on efficacy, safety (including dermal safety) and patch performance using the selected dose and administration.
- Patch size was developed that allows for rotation at a minimum of 2 sites to minimize local irritation at the application site of the knee.

## **9.7. Dose Adjustment Criteria**

Dose adjustment is **NOT** allowed in this study.

## **9.8. Drug Accountability**

The investigator or pharmacist, as appropriate, must maintain adequate records of the receipt and conditions of all study drugs, dispensing, return, or other disposition of study drug including the date, quantity dispensed to each subject, batch or code number, identification of subjects (subject number) who received study drug and any reasons for departure from the protocol-dispensing instructions. Receipt of study drug must also be confirmed within IWRS. The drug accountability records, along with dispensed and unused packaging must be available for monitoring, auditing, or inspection as deemed necessary.

The investigator will not supply study drug to any person except those named as sub-investigators (on the Form FDA 1572), designated study personnel, and subjects in this study. The investigator will not dispense study drug from any study sites other than those listed (on the Form FDA 1572).

Study drug may not be relabeled or reassigned for use by other subjects. If any of the study drug is not dispensed, is lost, stolen, unusable, or is received in a damaged container, this information must be documented and reported to Noven and appropriate regulatory agencies, as required.

At the completion of the study, a final reconciliation of all study drugs (dispensed, returned, used, and unused) must be performed by the site and only unused patches must be returned to the sponsor (or designated location). The unused study drug must be left in the original packaging and returned to the Sponsor (or designee) for destruction.

## **9.9. Treatment Compliance**

Treatment compliance with study drug regimens will be assessed by study personnel via the counting of returned unused patches, patch application, removal and by questioning the subject, if necessary, at every post-randomization visit. Treatment compliance will also be calculated as the number of patches applied divided by the prescribed number of patches over a given period, expressed as a percentage.

At Visits 4 through 8 or any Early Termination Visit, the study drug (patches) from the previous visit will be returned to the investigator. The study drug will be inventoried and non-compliance assessed as follows: use of less than 80% or more than 120% of study drug during any evaluation period (visit to visit). If the subject is non-compliant, and if there is a medically related need to do so, then the Medical Monitor should be contacted.

The subject must be counseled if compliance is not satisfactory (fail to apply the study drug on 2 or more consecutive days and/or miss any eDiary entries for 2 or more consecutive days). The subject must be contacted by a site personnel and re-instructed on how to apply the study drug and complete the eDiary. The re-instruction will be documented in the subject's chart (progress notes or clinical notes).

Subjects will be asked to record their daily intake/use of rescue medication/study drug in the eDiary. Deviations from the planned doses (overdose, missed dose or timing) will be recorded on the subjects' eCRF. The eDiaries will be constantly reviewed by study personnel.

## **9.10. Concomitant/Prior Therapies**

All medications used prior or during treatment (including OTC medications, herbal supplements, non-pharmacological activities [Exercise, Weight Loss, Tai Chi, etc.] and rescue medication) will be recorded in the source document and on the appropriate eCRF page. The Medical Monitor should be contacted if there are any questions regarding concomitant or prior therapy.

### **9.10.1 Permitted Therapies**

Glucosamine, chondroitin, and antidepressants (used for any indication other than pain) will be allowed if used as stable therapy for at least 90 days prior to Screening Visit. However, if used for less than 90 days, these drugs will be considered prohibited concomitant medications and will require a Washout Period. Subjects will be allowed to continue stable ASA therapy not for OA pain (up to 81 mg/day).

Other concomitant medications for treatment of ongoing medical conditions are allowed, but should be limited to those medications considered necessary in the opinion of the investigator.

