### 8.2.2 Exclusion Criteria

A subject will be excluded from the study if the he or she meets any of the following criteria:

- Body mass index (BMI)  $> 40 \text{ kg/m}^2$  at Screening (Visit 1).
- The non-target knee pain severity score is [REDACTED] at Screening (Visit 1) and Baseline (Day 0).
- Any subject who did not follow the restriction of prohibited therapies during Washout period (including use of rescue medication within 3 calendar days prior to the Baseline Visit).

4. Arthritis of the target knee that is not caused by OA but caused by diseases such as rheumatoid arthritis, gout, psoriasis, syphilitic arthropathy, ochronosis, metabolic or other primary bone disease, or acute traumatic injury.
5. Any subject diagnosed with fibromyalgia.
6. Any other painful or disabling conditions affecting the target knee or leg.
7. Clinically significant elevation of serum creatinine ( $\geq 2$  mg/dL), aspartate aminotransferase (AST) or alanine aminotransferase (ALT) (at  $3 \times$  upper limit of normal [ULN]) at the Screening Visit.
8. Known allergy or hypersensitivity to diclofenac, APAP, acetylsalicylic acid (aspirin [ASA]), or any other NSAID, [REDACTED], glycerin, propylene glycol, or ethanol.
9. Severe uncontrolled cardiovascular, renal, hepatic, or other systemic illness/disease.
10. A documented gastroduodenal ulcer (by upper GI series or endoscopy), GI perforation or any GI bleeding (except hemorrhoidal bleeding) within 6 months prior to Screening Visit.
11. Documented history of alcohol or drug abuse within 1 year prior to study entry or positive alcohol/drug screen findings at Screening or Baseline.
12. Presence of chondrocalcinosis on X-ray if associated with a history of pseudogout or inflammatory flare-ups.
13. MAJOR SURGERY: Previous damage or surgery to the target knee at any time (i.e., damage/reconstruction of the anterior or posterior cruciate ligaments).
14. MINOR SURGERY on the target knee defined as anything other than major surgery (as defined above) within 1 year before study enrollment.
15. Treatment with oral or intra-muscular corticosteroids within 90 days of Screening Visit, treatment of the target knee with topical or intra-articular corticosteroids within 90 days of Screening Visit, or topical or intra-articular corticosteroid treatment of any other joint within 30 days of Screening Visit.

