**Table 2 Prohibited Medications/Therapies**

Prohibited Medications/Therapies	Conditions
Any nonsteroidal anti-inflammatory drugs (NSAIDs) (selective or nonselective [Topical drug not for knees will be allowed]), acetaminophen (APAP) (>2 g/day), aspirin (ASA) (>81 mg/day), anticonvulsants (i.e., pregabalin and gabapentin etc.), muscle relaxants, other oral analgesics (prescription and/or over the counter [OTC]), antidepressants prescribed for the control of chronic pain syndromes, antihistamine with a sedative effect, sedatives for insomnia, topical products on the knee including methyl salicylate, camphor, menthol, methylsulfonylmethane, [REDACTED] [REDACTED] [REDACTED] capsaicin, any nonpharmaceutical therapy to relieve knee pain (physiotherapy, massage therapy, hot wax therapy, ice pack, acupuncture, thermal modalities, radiofrequency ablation, transcutaneous electrical nerve stimulation [TENS], pulsed vibration therapy, etc.), device to relieve knee pain (biofemoral bracing, kinesiotaping, modified shoes, wedged insoles etc.), hydroxychloroquine.	Prohibited during the study starting at Washout Visit
Any opioids, cannabinoids (prescribed or used recreationally), corticosteroids including oral, intra-muscular and intra-articular, topical, inhalation (a stable dose by inhalation for seasonal allergies and/or topical use for dermatologic allergies are allowed [Not allowed on the knees]), intra-articular viscosupplementation (e.g., Synvisc®), intra-articular drugs/biologics; anti-nerve growth factor agents, platelet rich plasma (PRP) injection, stem cells, prolotherapy, amniotic fluid injection, cyclosporine, lithium, or methotrexate	Prohibited during the study starting at Screening Visit
MAJOR SURGERY: Surgery to the target knee (i.e., damage/reconstruction of the anterior or posterior cruciate ligaments).  MINOR SURGERY: Surgery to the target knee defined as anything other than major surgery (as defined above)	Prohibited during the study starting at Screening Visit

Note: The investigator should contact the Medical Monitor with any concerns about the acceptability of any medication.

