**10.1.1.2 Washout Visit (Visit 2)**

The following procedures will be performed at the Washout Visit (V2):

1. Confirm subject's continued eligibility relative to inclusion/exclusion criteria.
2. Review eDiary NRS 11-point pain scores.   

██████████ will be entered to the eCOA system and the mean NRS scores will be calculated.

3. Record the eligibility of the subject in IWRS. If the subject screen fail, the date and the reason will be recorded in IWRS.
4. Placebo training will be performed to educate subjects. The aim is to minimize the placebo response and increase their awareness for the purpose of the trial to determine a new drug is effective and safe.
5. Subjects whose eligibility has been preliminarily confirmed will be asked to washout of their current medications for at least 7 days to a maximum of 14 days (or at least 5 half-lives, whichever is longer).
6. Subjects will be instructed by the site to stop taking all prescription and physician recommended OTC analgesic medications, but will be informed that rescue medication (i.e., APAP) may be used (a maximum of 2 g/day) as needed except **within 3 calendar days prior to the Baseline Visit (V3) and the day of Baseline Visit (V3)**.
7. Dispense rescue medication.
8. Ensure that the subjects have access to, and understands how to access and use, the eDiary.
9. Instruct the subject to continue to assess and record their target knee pain at home daily, using the NRS 11-point pain scale in the eDiary during the Washout Period.
10. Subjects will be instructed to record the number of tablets of rescue medication used, the time and the reason in the eDiary.

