- i QOL Questionnaire is Mini-OA Knee and Hip QOL (Mini-OAKHQOL) and Work Productivity and Activity Impairment Questionnaire for Osteoarthritis (WPAI: OA).
- j AEs will be collected starting from the first administered dose.
- k Screening visit (Visit 1) will be completed -28 to -10 days prior to Baseline Visit. Washout visit (Visit 2) is at least 3 days after Visit 1 (e.g. If Visit 1 is Day -10, Visit 2 can be scheduled on Day -7). Washout visit (Visit 2) will be completed -14 to -7 days prior to Baseline Visit. Washout Period will be initiated from the Washout Visit (Visit 2). Washout period is for 7 to 14 days.
- l Only for rescue medication.

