#### **14.2. Screen Failures**

Subjects who fail any of the inclusion and/or exclusion criteria may not be rescreened for the study. Retesting of clinical laboratory evaluations within the screening window is permitted (i.e., retesting of central clinical laboratory analytes can be done only once).

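### Section 9.10.1 requires a screened subject who wants to be randomized to stop a non-pain antidepressant used for under 90 days, and no safeguard asks whether stopping is safe

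*Protocol*

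**What the plan says.** The rule is in section 9.10.1, and its wording is the same in both protocol versions in the file. One sentence covers two supplements (glucosamine and chondroitin) together with a class of prescribed medicine: "antidepressants (used for any indication other than pain) will be allowed if used as stable therapy for at least 90 days prior to Screening Visit". For shorter use, the text is: "However, if used for less than 90 days, these drugs will be considered prohibited concomitant medications and will require a Washout Period".

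Four other places give the rule its effect:

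- **Exclusion criterion 3 (8.2.2)** removes "Any subject who did not follow the restriction of prohibited therapies during Washout period". Section 8.2 allows no exclusion criterion to be met and states no waiver.
- **Washout Visit, step 5 (10.1.1.2)** sets the length: at least 7 days to "a maximum of 14 days (or at least 5 half-lives, whichever is longer").
- **Schedule of Events, note k (10.2)** sets the earliest timing: "Washout visit (Visit 2) is at least 3 days after Visit 1".
- **Section 14.2** limits second attempts: "Subjects who fail any of the inclusion and/or exclusion criteria may not be rescreened for the study".

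Two places that a site would consult do not carry the rule. Among antidepressants, Table 2 names only "antidepressants prescribed for the control of chronic pain syndromes". Step 6 of the Washout Visit tells subjects to "stop taking all prescription and physician recommended OTC analgesic medications", which does not cover an antidepressant taken for a non-pain illness.

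**The concern.** Stopping glucosamine or chondroitin and stopping an antidepressant in its first three months are different clinical acts, yet one sentence governs both. The antidepressant was started for another illness, and the protocol makes ending it a step towards entering a placebo-controlled patch trial in knee osteoarthritis.

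The issue is subject protection during washout. The 90-day rule serves a reasonable purpose, which is to avoid a changing antidepressant during the pain assessments. Not enrolling these subjects until they are stable serves that purpose equally well and withdraws nothing.

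The protocol already takes that approach elsewhere. Exclusion 20 makes a subject who needs cyclosporine, lithium or methotrexate ineligible; it does not wash the drug out. The last sentence of 9.10.1 itself permits other medicines that the investigator judges necessary for ongoing conditions.

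**Working it through.** The plan states no figure on this point, so there is none to reproduce. The check is a reading of the text plus day arithmetic.

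**1. Does the text lead to stopping?** The 90 days are counted back from Screening. Screening is 10 to 28 days before Baseline, and that interval does not count towards the 90.

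- A subject with 89 days of use at Visit 1 would have 89 + 10 = 99 to 89 + 28 = 117 days by Baseline if the drug were continued, and still does not meet the rule.
- A subject with 62 days at Visit 1 could reach 62 + 28 = 90 days by Baseline at most, and does not meet it either.

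The drug is then prohibited and needs washout. Keeping it through washout meets exclusion 3. A screened subject who wants to continue to randomization must therefore stop.

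**2. When does the stop fall?** Visit 1 is Day -28 to -10 and Visit 2 is Day -14 to -7.

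- Minimum: Day -10 to Day -7 = 3 days after Screening.
- Maximum: 28 - 7 = 21 days after Screening.

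**3. How long is the subject off the drug?** Assume a completer, a 7 to 14 day washout, the prohibition lasting to Visit 8, and no need to restart treatment.

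- Nominal: 7 + 84 = 91 days to 14 + 84 = 98 days.
- With the Visit 8 window of ±7 days: 7 + 77 = 84 days to 14 + 91 = 105 days.
- Five half-lives exceed 14 days when the half-life is above 14 / 5 = 2.8 days. Step 5 then asks for a longer washout, while note k still gives 7 to 14 days. The two do not agree for such drugs.

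**4. Does any safeguard ask whether stopping is safe?**

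| Provision | What it asks |
|---|---|
| Section 10, opening | Written consent before prohibited therapy is stopped |
| Visit 1, steps 5 and 6 | Record of current therapies; documented rationale for taking part if there is a psychiatric condition; psychiatric component of the examination |
| Exclusion 26, eligibility re-confirmed at Visits 2 and 3 | Whether a psychiatric condition may interfere with participation |
| 9.10 and the note under Table 2 | Medical Monitor contact for questions, or for concerns about whether a medicine is acceptable |
| Visit 2 and Visit 3 procedure lists | No taper, prescriber contact or mood assessment listed |

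The first four would let a careful investigator stop the process. None puts the question of safe withdrawal.

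**5. Where are washout events recorded?** AE collection starts at the first dose (11.2). Conditions that arise between consent and dosing go to medical history (11.1.1; SAP section 11). They are recorded, but nothing marks them as following from the entry rule.

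**The case against.** The strongest reply is that this is ordinary clinical judgement. At Visit 1 the investigator records current therapies and, for any psychiatric condition, must document why participation is appropriate; participation includes the washout. Consent is specifically required before therapy is stopped, exclusion 26 is re-checked twice, and the Medical Monitor can be consulted about any medicine. The consent form was not available for this review and may say more. No rate of use, relapse or withdrawal is given, so the number affected could be zero. Most of this stands. It shows that a careful site can avoid the problem. It does not explain why the protocol should direct the withdrawal when ineligibility would serve the same purpose.

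A reader might infer more than the documents support:

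- **That stopping must be abrupt.** Nothing forbids a taper, and Visit 2 may be up to 21 days after Visit 1.
- **That a screened subject who keeps the drug is barred for good.** Section 14.2 applies to subjects who fail a criterion. No legible criterion in 8.2.1 or 8.2.2 names recent non-pain antidepressant use, and exclusion 3 concerns conduct during washout. A subject who withdraws at Visit 1 has not clearly failed anything. A site may also delay consent until 90 stable days have passed.
- **That psychiatric safeguards are absent.** They exist; they are general.
- **That washout events go unrecorded.** They are entered as medical history, coded and summarized.
- **That the HP-5000 versus placebo comparison is biased.** The withdrawal comes before randomization, and nothing in the documents suggests that it acts differently in the two arms.

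**Conclusion.** The point holds as a narrow one about subject safety. Section 9.10.1 states a rule, enforced by exclusion 3, under which a screened subject who wants to be randomized must stop a recently started antidepressant taken for another illness. The subject remains free to decline or wait. The general safeguards do not ask whether stopping is safe. Because the rule is absent from Table 2 and from the Visit 2 stop instruction, sites may also apply it differently.

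For each affected subject, the stop comes 3 to 21 days after Screening and lasts a nominal 91 to 98 days under the assumptions in the working, longer if five half-lives exceed 14 days. The number of such subjects is unknown and probably small. The change is worth making because it removes an unnecessary risk at little cost. It is not a validity problem, and no effect on the primary analysis is claimed.

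**What to change.** 1. In 9.10.1, keep the under-90-day washout for glucosamine and chondroitin only. State that a subject who has used an antidepressant for a non-pain indication for less than 90 days before Screening is not eligible, and that the drug must not be stopped to qualify.
2. Add the matching exclusion to 8.2.2 and to its copy in the synopsis.
3. Add a cross-reference to 9.10.1 in Table 2, so that a site relying on the table finds the rule.
4. Optionally, amend 14.2 to allow one rescreen after 90 stable days.

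The new exclusion should turn on duration of use, as the present washout sentence does. Wording it as not stable for 90 days would also exclude long-term users with a recent dose change, which is a separate decision.

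Cost: a protocol amendment with IRB review, and no SAP change. An unknown but probably small number of subjects are lost or deferred. With d days of use at Screening (0 to 89), the wait is 90 - d, so 1 to 90 days. If step 4 is adopted, each rescreened subject repeats the Visit 1 and Visit 2 procedures, and the IWRS must allow it.

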### **9.10.2 Prohibited Therapies**

Prohibited medications/therapies are presented in **Table 2**.

**Table 2 Prohibited Medications/Therapies**

Prohibited Medications/Therapies	Conditions
Any nonsteroidal anti-inflammatory drugs (NSAIDs) (selective or nonselective [Topical drug not for knees will be allowed]), acetaminophen (APAP) (>2 g/day), aspirin (ASA) (>81 mg/day), anticonvulsants (i.e., pregabalin and gabapentin etc.), muscle relaxants, other oral analgesics (prescription and/or over the counter [OTC]), antidepressants prescribed for the control of chronic pain syndromes, antihistamine with a sedative effect, sedatives for insomnia, topical products on the knee including methyl salicylate, camphor, menthol, methylsulfonylmethane, [REDACTED] [REDACTED] [REDACTED] capsaicin, any nonpharmaceutical therapy to relieve knee pain (physiotherapy, massage therapy, hot wax therapy, ice pack, acupuncture, thermal modalities, radiofrequency ablation, transcutaneous electrical nerve stimulation [TENS], pulsed vibration therapy, etc.), device to relieve knee pain (biofemoral bracing, kinesiotaping, modified shoes, wedged insoles etc.), hydroxychloroquine.	Prohibited during the study starting at Washout Visit
Any opioids, cannabinoids (prescribed or used recreationally), corticosteroids including oral, intra-muscular and intra-articular, topical, inhalation (a stable dose by inhalation for seasonal allergies and/or topical use for dermatologic allergies are allowed [Not allowed on the knees]), intra-articular viscosupplementation (e.g., Synvisc®), intra-articular drugs/biologics; anti-nerve growth factor agents, platelet rich plasma (PRP) injection, stem cells, prolotherapy, amniotic fluid injection, cyclosporine, lithium, or methotrexate	Prohibited during the study starting at Screening Visit
MAJOR SURGERY: Surgery to the target knee (i.e., damage/reconstruction of the anterior or posterior cruciate ligaments).  MINOR SURGERY: Surgery to the target knee defined as anything other than major surgery (as defined above)	Prohibited during the study starting at Screening Visit

Note: The investigator should contact the Medical Monitor with any concerns about the acceptability of any medication.

### 9.10.3 Concomitant Medication Cautions

Investigator's clinical judgment will be used in the following situations (the Medical Monitor for the study may be contacted if necessary);

- Angiotensin-converting enzyme (ACE) inhibitors, angiotensin receptor blockers (ARB) or beta-blockers: Concomitant use with HP-5000 may diminish the antihypertensive effect of these drugs. Monitor blood pressure.
- ACE Inhibitors and ARBs: Concomitant use with HP-5000 in elderly, volume depleted, or those with renal impairment may result in deterioration of renal function. In such high risk subjects, monitor for signs of worsening renal function.
- Diuretics: NSAIDs can reduce natriuretic effect of furosemide and thiazide diuretics. Monitor subjects to assure diuretic efficacy including antihypertensive effects.
- Digoxin: Concomitant use with HP-5000 can increase serum concentration and prolong half-life of digoxin. Monitor serum digoxin levels.

